8.4.5 Blood product/adjunct use

The amount of blood products used, over the first 24h since injury, are collected:

- a) Red cell concentrate (units)
- b) Plasma (units)
- c) Platelets (pools)
- d) Whole blood (units)
- e) Cryoprecipitate (units)

f) Tranexamic acid (grams)

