110	sponges_removed_dt_tm_2 Show the field ONLY if: [randomized_yn] = '1' and [xst at_attempted] = '1' and [suta proc_wound(2]] = '1' and [xsta t_used_wound_2] = '1'	Section Header: Please describe the experience removing the XSIAT sponges from the wound to the [wound,2,ide], [wound,2, orientation] [wound,2,loc]: What was the date and time at which the sponges were finally removed (or when decision was made that they could not be removed? (M-D-Y H:M)	text (datetime_mdy)
111	ease_sponge_remove_2 Show the field ONLY if: [randomized_yn] = '1' and [xst at_attempted] = '1' and [surg_ proc_wound[2]] = '1' and [xsta t_used_wound_2] = '1'	Please describe the ease of sponge removal	radio 1 Failed to remove all sponges 2 Reasonably easy to remove all sponges 3 Sponges easily removed
112	time_sponge_removal_2 Show the field ONLY if: [randomized_yn] = '1' and [xst at_attempted] = '1' and [surg_ proc_wound[2]] = '1' and [xsta t_used_wound_2] = '1'	Please estimate the time required to remove the sponges	radio 1 31 minutes or longer 2 Between 5 and 30 minutes 3 Less than 5 minutes
113	imaging_sponge_removal_2 Show the field ONLY if: [randomized_yn] = '1' and [xst at_attempted] = '1' and [surg_ proc_wound(2]] = '1' and [xsta t_used_wound_2] = '1'	Please describe what intraoperative imaging was used to ensure removal of the sponges	radio 1 Imaging not used due to patient's condition 2 Imaging not used, as not available 3 Imaging not used, as deemed unnecessary 4 Imaging used
114	Imaging_outcome_2 Show the field ONLY if: [randomized_yn] = '1' and [sst at_attempted] = '1' and [srt proc_wound[2] = '1' and [ima ging_sponge_removal_2] = '4' and [ixstat_used_wound_2] = '1'	Describe the outcome	radio 1 Additional sponges were seen on imaging 2 No additional sponges were seen on imaging

115	xstat_satisfaction_2 Show the field ONLY if:	Please describe your overall satisfaction with the XSTAT device	radio 1 Dissatisfied
	[randomized_yn] = '1' and [xst at attempted] = '1' and fourg		2 Neither satisfied nor dissatisfied
	proc_wound(2)] = '1' and [xsta t_used_wound_2] = '1'		3 Satisfied
116	form_7_operative_treatment_	Section Header: Form Status	dropdown
	complete	Complete?	0 Incomplete
			1 Unverified
			2 Complete
Instr	rument: Form 8: Blood/Blo	od Product Transfusion Record (form_8_bloodblood_pro	duct_transfusion_record)
117	header_f8		descriptive
118	red_cell_units	Red cell concentrate (units)	text (integer) Field Annotation: @DEFAULT="0"

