119	plasma_units	Plasma (units)	text (integer) Field Annotation: @DEFAULT="0"
120	platelet_units	Platelets (units)	text (integer) Field Annotation: @DEFAULT="0"
121	cryo_units	Cryoprecipitate (units)	text (integer) Field Annotation: @DEFAULT="0"
122	whole_blood_units	Whole blood (units)	text (integer) Field Annotation: @DEFAULT="0"
123	form_8_bloodblood_product_	Section Header: Form Status	dropdown
	transfusion_record_complete	Complete?	0 Incomplete
			1 Unverified
			2 Complete
Instr	rument: Form 9: Procoagul	ant medication (form_9_procoagulant_medication)	A Collapse
124	header_f9		descriptive
125	txa_mg	Tranexamic acid (mg)	text (number) Field Annotation: @DEFAULT="0"
126	fibrinogen_mg	Fibrinogen concentrate (mg)	text (number) Field Annotation: @DEFAULT="0"
127	octaplex_mg	Octaplex (mg)	text (number) Field Annotation: @DEFAULT="0"
128	prothrombin_complex	Prothrombin complex concentrate	text (number) Field Annotation: @DEFAULT="0"
129	vitamin_k	Vitamin K	text (number) Field Annotation: @DEFAULT="0"
130	other_procoag_med	Other (specify, including amount)	notes
131	form_9_procoagulant_medica	Section Header: Form Status	dropdown
	tion_complete	Complete?	0 Incomplete
			1 Unverified
	1		
			2 Complete
Instr	rument: Form 10: Admissio	n Blood Work (form_10_admission_blood_work)	2 Complete
Instr 132	rument: Form 10: Admissio	n Blood Work (form_10_admission_blood_work)	2 Complete Collapse descriptive
Instr 132 133	rument: Form 10: Admissio header_f10 blood_gas_source	n Blood Work (form_10_admission_blood_work) Section Header: From blood gas analysis:	2 Complete Collapse descriptive radio
Instr 132 133	rument: Form 10: Admission header_f10 blood_gas_source	n Blood Work (form_10_admission_blood_work) Section Header: From blood gas analysis: Source	2 Complete Collapse descriptive radio 1 Arterial
Instr 132 133	rument: Form 10: Admission header_f10 blood_gas_source	n Blood Work (form_10_admission_blood_work) Section Header: From blood gas analysis: Source	2 Complete Collapse descriptive radio 1 Arterial 2 Venous
Instr 132 133	rument: Form 10: Admissio header_f10 blood_gas_source	n Blood Work (form_10_admission_blood_work) Section Header: From blood gas analysis: Source	2 Complete A Collapse
Instr 132 133 134	rument: Form 10: Admissio header_f10 blood_gas_source lactate	n Blood Work (form_10_admission_blood_work) Section Header: From blood gas analysis: Source Lactate (mmol/L)	2 Complete Collapse descriptive radio 1 Arterial 2 Venous text (number)

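### All ten amount fields on Forms 8 and 9 are pre-filled with 0, so an unrecorded amount can be stored as none given; platelets and tranexamic acid also have conflicting units

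*Protocol*

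**What the plan says.** Protocol section 8.4.5 asks for six amounts over the first 24 hours after injury: red cells, plasma, platelets, whole blood, cryoprecipitate and tranexamic acid. Table 1 (section 8.5) places blood products at 24 hours in the feasibility block.

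Appendix 2 sets out how these are stored. Each of the five Form 8 fields is defined as "text (integer) Field Annotation: @DEFAULT='0", and each of the five numeric Form 9 fields as "text (number) Field Annotation: @DEFAULT='0". All ten thus carry "Field Annotation: @DEFAULT='0", and no other attribute is given for any of them.

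The units are stated twice:

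- Platelets are "Platelets (pools") in section 8.4.5 and "Platelets (units") on Form 8.
- Tranexamic acid is "Tranexamic acid (grams") in section 8.4.5 and "Tranexamic acid (mg") on Form 9.

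Section 8.2 says that data go first onto paper and are then transcribed to the electronic form. It provides for logic checks, an audit of a random 20% of subjects, and resolution of doubtful entries before lock. Section 15.2 adds monitors who compare study records with source documents.

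**The concern.** A field that starts at 0 is never blank. If a form is opened and saved before the transfusion record has been abstracted, the stored value says that nothing was given. A completeness check passes. A logic check has no reason to object, because 0 is a legal and often correct value. The form-status item (incomplete, unverified, complete) describes the whole form, not whether a given 0 was typed or pre-filled.

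This cannot be left to the statistical analysis plan. Once a missing amount has been exported as 0, nothing marks it as missing and no missing-data method can be applied to it.

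What is at stake is the estimate of early blood-product and procoagulant use in patients who enter with class 3 or 4 hemorrhagic shock. Objective 2 seeks baseline estimates for planning a full trial. A downward bias would carry into that planning. If record quality differs between arms, it could also appear as a difference between them.

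The unit conflict is a second, independent problem. Someone who fills in paper according to section 8.4.5 writes grams and pools, while the database expects mg and units.

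**Working it through.** **1. Fields with a zero default (Appendix 2).**

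- Form 8: red cells, plasma, platelets, cryoprecipitate, whole blood. 5 of 5.
- Form 9: tranexamic acid, fibrinogen concentrate, Octaplex, prothrombin complex concentrate, vitamin K. 5 of 5.
- Total: 10 of 10. Required flag: 0 of 10. Range limit: 0 of 10. Code for not known: 0 of 10.

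The same codebook uses these devices elsewhere. The Form 10 laboratory fields have no default. Site and mechanism of injury are required. Systolic pressure is limited to 0–220 and hematocrit to 0–100. Gender and birth year allow unknown.

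**2. Units, section 8.4.5 against the codebook.**

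| Amount | Section 8.4.5 | Codebook | Agree |
|---|---|---|---|
| Red cells | units | units | yes |
| Plasma | units | units | yes |
| Whole blood | units | units | yes |
| Cryoprecipitate | units | units | yes |
| Platelets | pools | units | no |
| Tranexamic acid | grams | mg | no |

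Two of six conflict. The other four Form 9 drugs are not listed in section 8.4.5, so they have no unit there to conflict with.

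**3. Size of the bias from false zeros (illustration only).** The protocol gives no transfusion mean and no missing rate. With true mean μ and a share m of records wrongly stored as 0 (taken as unrelated to the true amount), the recorded mean is (1 − m) × μ. Assume μ = 6 units:

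- m = 5%: 0.95 × 6 = 5.7
- m = 10%: 0.90 × 6 = 5.4
- m = 20%: 0.80 × 6 = 4.8

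With the same m and the same μ in both arms there is no false difference. If m were 10% with XSTAT and 30% in control, the recorded means would be 5.4 and 0.70 × 6 = 4.2, a false difference of 1.2 units.

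**4. What the audit would find.** Section 9 gives a maximum of 50 patients, and section 8.2 an audit of 20%, which is 10 records. With k faulty records, the chance that the audit sees none is C(50 − k, 10) / C(50, 10):

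| k | Probability of missing all |
|---|---|
| 1 | 0.80 |
| 2 | 0.64 |
| 3 | 0.50 |
| 5 | 0.31 |

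An audit that finds one faulty record still leaves 40 unaudited.

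**5. Grams entered in the mg field.** Such a record is too small by a factor of 1000. If a share g of records is so entered and all patients truly received the same amount, the recorded mean is (1 − g) + g/1000 of the true one: about 0.96, 0.90 and 0.80 for g = 4%, 10% and 20%. These shares are assumptions. For platelets the error depends on how many donor units make up a pool, which the protocol does not state.

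**The case against.** The strongest reply is that these are possibilities, not errors in data. Each database field has a single labelled unit, so a 1000-fold error requires someone to disregard the label on the screen. Logic checks, query resolution before lock, the audit and source monitoring (sections 8.2 and 15.2) all exist. Section 15.1.2 describes a procedures manual that defines every study variable and may define a platelet unit. The header text of Forms 8 and 9 is not shown and may contain entry instructions. Section 16.2.1 calls the Appendix 2 form a sample and foresees testing and finalizing the forms, although section 8.2 cites the same appendix as the case report form. The trial is a pilot with no primary outcome.

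Much of this limits the point, and four stronger readings should be set aside:

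- A reader might infer that the forms depart from the protocol's units in general. They do so for two of six amounts.
- A reader might infer that mis-scaled values will enter the analysis. The documents show only a risk at transcription.
- A reader might infer that blood use is one of few measures available in both arms. Sections 8.4.1 and 8.4.3 to 8.4.6 list many others, among them vital signs, lactate, base deficit, coagulation tests, survival and length of stay.
- A reader might infer that transfusion is a specified outcome. Section 7 does not name it, Objective 2 names lactate, base deficit and mortality in an open list, and section 10.4 compares only specified outcomes. Its role is inferred from section 8.4.5 and Table 1.

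What the reply does not remove is the default itself. A plausible 0 does not look doubtful, so logic checks and queries will usually pass it. Source comparison finds it only in the records compared.

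**Conclusion.** The point stands as a modest data-capture weakness that is worth correcting before enrollment. All ten numeric amounts on Forms 8 and 9 can hold a zero that means not recorded, and the stored data cannot show which zeros those are. The likely direction is downward, in a data set of at most 50. Two recording units, for platelets and tranexamic acid, contradict each other between section 8.4.5 and the codebook and must be reconciled.

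The size is not known. The figures of 4.8 to 5.7 units against 6, and the 1.2-unit false difference, rest on an assumed mean and assumed missing rates. The difference between arms needs unequal missingness, for which the protocol gives no evidence; equal rates would shrink a true difference, not create one. The audit probabilities assume full enrollment of 50 and one random audit of 10 records. The conclusion also assumes that a form opened and saved keeps its default. The protocol does not say what happens to a form that is never opened.

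**What to change.** - Remove the zero default from all ten fields on Forms 8 and 9.
- Then require an entry in each, with a separate not-known option. The order matters: a required flag has no effect while 0 is already filled in.
- Add range checks. For tranexamic acid the check should accept 0 but query a non-zero value too small to be in mg, since an upper limit alone would not catch grams.
- Use one recording unit for platelets and one for tranexamic acid in section 8.4.5, on the paper form and in the codebook. State whether a platelet unit means a pool or apheresis dose, or a single-donor unit.

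The cost is a small form edit and a few more keystrokes per patient. The codebook is dated April 2019 and section 16.2.2 starts enrollment in month 13, so the change fits within the planning phase. If any patients are already entered, their zeros on these two forms should be checked against source.
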